5.3.3 Concomitant medication date imputation

Impute CM end date:

1. If CM end day is missing and CM month/year are non-missing then impute CM day as the minimum of treatment end date (date of the last dose) and the last day of the month.
2. If CM end day/month are missing and CM year is non-missing then impute CM day as the minimum of treatment end date and the end of the year (31DECYYYY).
3. If imputed CM end date is less than the CM start date, use the CM start date as the imputed CM end date.

Impute CM start date:

1. If the CM start date year value is missing, the imputed CM start date is set to one day prior to treatment start date.
2. If the CM start date year value is less than the treatment start date year value, the CM started before treatment. Therefore:
 - a. If the CM month is missing, the imputed CM start date is set to the mid-year point (01JULYYYY)
 - b. Else if the CM month is not missing, the imputed CM start date is set to the mid-month point (15MONYYYY)
3. If the CM start date year value is greater than the treatment start date year value, the CM started after treatment. Therefore:

- a. If the CM month is missing, the imputed CM start date is set to the year start point (01JANYYYY)
- b. Else if the CM month is not missing, the imputed CM date is set to the month start point (01MONYYYY)

4. If the CM start date year value is equal to the treatment start date year value:
 - a. And the CM month is missing or the CM month is equal to the treatment start date month, then the imputed CM start date is set to one day prior treatment start date
 - b. Else if the CM month is less than the treatment start date month, the imputed CM start date is set to the mid-month point (15MONYYYY)
 - c. Else if the CM month is greater than the treatment start date month, the imputed CM start date is set to the month start point (01MONYYYY)

If complete (imputed) CM end date is available and the imputed CM start date is greater than the (imputed) CM end date, then imputed CM start date should be set to the (imputed) CM end date.

5.3.3.1 Prior therapies date imputation

See Section 5.3.3

5.3.3.2 Post therapies date imputation

See Section 5.3.3

5.4 AEs coding/grading

Adverse events will also be coded according to MedDRA dictionary, using a narrow search. The MedDRA version used for reporting the adverse events will be described in a footnote. Safety topics of interest, such as risks defined in the Safety Profiling Plan, Risk Management Plan or topics of interest regarding signal detection or routine analysis are defined in the Program Case Retrieval Sheet.

5.5 Statistical models

Primary analysis

This section provides the details of model stated in Section 2.5.

5.5.1.1 Logistic regression

Certain binary outcome variables, e.g. response outcomes, will be evaluated using a logistic regression model with treatment as factor and weight as a covariate. The marginal standardization method will be used to calculate the mean response rate in each treatment group as well as their difference. This method uses the same fitted logistic model, but involves using the model to predict, for each patient in the study, the mean outcome assuming assignment to each particular treatment group in turn, assuming each patient's observed values for the other baseline covariates (i.e., weight). Averaging these predictions for each treatment group provides

the estimate of the mean response rate for each treatment group. Then the difference will be derived based on the estimated mean response rates comparing s.c. regimen vs. placebo.

SAS code example as the following,

```
options validvarname=v7;  
%Margins(data      = mydata,  
         class     = treatments strata,  
         response  = AVAL,  
         roptions  = event = '1',  
         model    = treatment baseline_weight strata,  
         dist     = binomial,  
         margins  = treatment,  
         options   = cl diff)
```

If convergence is not obtained the following sequential steps will be used:

1. Remove *strata*. If still no convergence, perform exact test

When exact test is applied, the risk difference and confidence intervals will be estimated via PROC FREQ and EXACT statement.

Input dataset should only contain data from the two treatment groups to be compared.

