2.5.2 Statistical hypothesis, model, and method of analysis

The primary analysis will be conducted via logistic regression with treatment and stratification factor (CRP+/MRI+, CRP+/MRI-, CRP-/MRI+) as factors and weight as a covariate. Difference in marginal response proportions between secukinumab regimen and placebo regimen and the corresponding 95% confidence interval (CI) will be computed utilizing the logistic regression model fitted.

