5.5.1.2 Sensitivity analysis

5.5.1.2.1 Multiple imputation

Under MAR assumption

A linear regression model will be used to perform multiple imputation (MI) under a missing-at-random (MAR) assumption. To help preserve the relationship between outcome and covariates within each treatment a separate model will be run for each treatment. This will also help ensure that the imputation model does not make stronger assumptions on data relations than the analysis model.

The SAS code below outlines a template for the analysis where covariates and visits can be added or removed as required. To ensure that results can be replicated the data should be sorted by subject number before running the model (the data should be in horizontal format with one subject per dataset row).

```
proc mi data= seed=4572301 nimpte=100 out=mi_out;  
by treatment;  
class strata;  
fcs reg (/details);  
var strata weight value1 value2 value3;
```

run;

Where in the template code the continuous variable to be imputed is *value* (e.g. *value1* could be the baseline value and *value2* the first post-treatment measurement of the variable to be imputed.) Normally, all data collection visits during the analysis period of interest would be included in the model. Including variables using a CLASS statement instead of a BY statement should help facilitate model convergence also when the number of non-missing data points are low for some specific covariate level and visit combination. The FCS option is used to ensure that also non-monotone missing data can be handled in an appropriate way.

If convergence is not obtained the following sequential steps will be used:

1. Remove *weight*.

For a situation where several variables need to be imputed using separate models (e.g., using independent models to impute each component needed to derive a response variable *V*) a stepwise process needs to be implemented as outlined below:

1. Run the SAS code as described above for the first variable to be imputed
2. Run the SAS code as described above for the next variable to be imputed (but with the following changes: “data=*mi_out*”, “out=*mi_out2*”, “by *treatment_imputation_*”, “nimpute=1”)
3. Repeat step 2, but with input dataset equal to the output dataset from the prior step, until all *j* variables have been imputed resulting in a dataset named *mi_outj*
4. Derive the variable *V* from within *mi_outj*

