5.5.1.5.3 Mixed-effects repeated measures model

Some endpoints will be analyzed using a longitudinal model that comprises several visits. The model used will be mixed model repeated measures (MMRM) with factors, covariates, interactions and covariance structure as specified for respective analysis. The SAS code below outlines a template for the analysis where covariates and interaction terms can be added or removed as required:

```
ods output diff=lsm_diff lsmeans=lsm_est;  
proc mixed data=;  
class treatment strata visit;  
model outcome=treatment strata visit baseline weight treatment * visit  
baseline * visit / ddfm=kr;  
repeated visit / type=un subject=;  
lsmeans treatment * visit / diff cl;  
run;
```

Least-square-mean (LSM) estimated for each treatment group and LSM difference, confidence intervals and p-value for the difference between each dose of secukinumab and placebo, and between secukinumab doses if relevant, can be obtained.

In case the MMRM model does not converge the following sequential steps will be used:

1. Change to ddfm=bw. If still no convergence, perform step 2.
2. Change to type=cs. If still no convergence, perform step 3.
3. Remove covariates in the following order until convergence: *weight, baseline*visit, strata*

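### The SAP's detailed text for the primary logistic model omits the randomisation stratum that its own code and main text include, and its non-convergence rule has no stratified step

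*SAP*

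**What the plan says.** **Main text.** SAP 2.5.2 specifies "logistic regression with treatment and stratification factor (CRP+/MRI+, CRP+/MRI-, CRP-/MRI+) as factors and weight as a covariate". Protocol 12.4.2 says the same. SAP 2.6.2 includes the stratum in the model for every secondary responder endpoint.

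**Detailed text.** SAP 5.5 introduces its primary-analysis part with "This section provides the details of model stated in Section 2.5". Section 5.5.1.1 then describes a "logistic regression model with treatment as factor and weight as a covariate". For the marginal standardisation it uses each patient's "observed values for the other baseline covariates (i.e., weight"; weight is the only covariate named in that bracket.

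**Code in the same section.** The SAS example lists the stratum as a class variable and fits "treatment baseline_weight strata".

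**Non-convergence.** Section 5.5.1.1 first removes the stratum. Then: "If still no convergence, perform exact test", with the risk difference and interval taken from PROC FREQ and no stratum mentioned. Non-convergence is not defined.

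**Reach.** SAP 5.5.1.4.2 applies 5.5.1.1 to the other responder endpoints. SAP section 4, which lists departures from the protocol, does not mention dropping the stratum.

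**The concern.** A programmer is likely to work from section 5.5, and its text and code specify different primary models. Participants are randomised within the three CRP/MRI strata. An analysis that ignores the strata gives a standard error that is somewhat too large and leaves chance imbalance unadjusted. Such imbalance is possible in the TNF-naive primary population because TNF status is not itself a randomisation factor. The success criteria in the sample-size section compare the observed difference with 6.15 percentage points and with 0, so which model produces that difference should not be open to interpretation.

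The fallback matters for endpoints with few responders. If a stratum has none, the stratified logistic likelihood has no finite maximum, and the plan then abandons stratification altogether. A stratified risk difference would remain computable without an iterative fit.

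**Working it through.** **1. The plan's own figures.** Inputs from SAP 3.1: 60 TNF-naive participants per arm, ASAS40 rates 0.415 and 0.292. With X1 ~ Bin(60, 0.415) and X0 ~ Bin(60, 0.292), P((X1 - X0)/60 > 0.0615) = 0.773 and P(X1 > X0) = 0.907. These equal the tabulated 0.773 and 0.907, and the other three scenarios also match. No stated figure is disputed.

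**2. Which model is meant.** Four places include the stratum: protocol 12.4.2, SAP 2.5.2, the 5.5.1.1 code, and the 5.5.1.1 instruction to remove it on failure. Two phrases in the 5.5.1.1 prose leave it out. The phrases are therefore the error.

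**3. How often the fallback is reached.** Stratum shares are not given, so the smallest stratum was assumed to hold 33%, 15% or 5% of participants. For a stratum with m participants per arm, P(no responders) = (1 - p1)^m (1 - p0)^m.

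- ASAS40, 15% share, m = 9: (0.585 × 0.708)^9 = 0.0004. At a 5% share, m = 3: 0.071.
- Sparse endpoint, assumed 20% vs 7% in 134 participants, 15% share, m = 10.05: (0.80 × 0.93)^10.05 = 0.051.
- A placebo arm with no responders at all, 67 participants: 0.93^67 = 0.008; at an assumed 3%, 0.97^67 = 0.130.

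Simulating the full model (1,500 trials per setting, separation counted as failure, weight not prognostic) gave the failure rates below. The lower figure is for non-prognostic strata, the higher for assumed stratum log-odds of 0, -0.8 and -0.4.

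| Endpoint | Smallest stratum 33% | 15% | 5% |
|---|---|---|---|
| ASAS40, 41.5% vs 29.2%, N = 120 | 0% | 0.2-0.4% | 12-26% |
| Assumed 20% vs 7%, N = 134 | 0.9-2.9% | 6-17% | 39-58% |
| Assumed 10% vs 3%, N = 134 | 24-30% | 38-52% | 71-82% |

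A separate simulation with assumed strata of 60, 27 and 47 and rates of 20% vs 5% gave 6% failures with non-prognostic strata, and 32% if the CRP+/MRI- rate is 0.3 of the others.

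**4. What rescues a failing fit.** At 20% vs 7% with a 15% stratum, 97 and 251 of 1,500 fits failed. Dropping weight rescued none of them. Dropping the stratum rescued all but 13 and 10.

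**5. Size of the effect.**
- Simulated ASAS40 standard error without versus with the stratum, equal strata: 0.0857/0.0850 = 1.008 (not prognostic) and 0.0858/0.0841 = 1.020 (prognostic).
- Stronger stratum effects: the ratio of interval widths is the square root of total over within-stratum binomial variance. With strata 60/27/47 and rates 0.45, 0.20, 0.35, √(0.2317/0.2229) = 1.020. With 0.50, 0.15, 0.35, √(0.2348/0.2174) = 1.039.
- Point estimate: the two models differed on average by 0.1-0.2 percentage points with strata balanced by randomisation. Allowing imperfect balance in the TNF-naive subset, the average was 0.3-0.7 points, and the estimates fell on opposite sides of 6.15 points in about 1-3% of trials.

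**The case against.** The strongest reply is that this is a wording slip. The code and the step removing the stratum show that the stratified model is planned, 5.5.1.4.2 tells the analyst to use the factors specified for each endpoint, and section 4 records no change. That stands: a reader might infer that the primary analysis is planned without the stratum, and the documents do not support it.

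Other stronger readings also fail:

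- **That the fallback contradicts SAP 2.5.2.** That section gives no convergence rule. Only the model prose conflicts with it.
- **That the removal order is the fault.** The MMRM rule ("Remove covariates in the following order until convergence") starts with weight and ends with the stratum, and the multiple-imputation rule ("If convergence is not obtained the following sequential steps will be used") removes only weight. Both concern continuous outcomes, where a stratum without responders cannot arise. In the logistic model the stratum term is usually what fails, and removing weight first rescued no simulated fit.
- **That the stratum subgroup analyses in SAP 2.2.1 suffer.** Within one stratum there is no stratum term to lose.
- **That the exact method should go.** It remains a sensible last resort, particularly within a single stratum.

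It is also fair that wider intervals are conservative, that the study estimates rather than tests, and that interval width does not enter the tabulated success criteria. This limits the importance of the point. It does not excuse an operational description of the primary model that differs from its code.

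**Conclusion.** Two things hold. First, the prose of SAP 5.5.1.1 misstates the primary model by omitting the stratum, in conflict with the protocol, SAP 2.5.2 and its own code. Second, the non-convergence rule has no step that keeps stratification, and it leaves non-convergence undefined.

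The consequence is modest: intervals about 1-4% wider and generally sub-point average shifts in the ASAS40 difference. The fallback is rarely reached for ASAS40 unless one stratum is very small. It is plausible for sparse endpoints such as ASAS partial remission in the FAS: roughly 1-17% of trials at 20% vs 7% with the smallest stratum at 15-33%, and more if strata are smaller or strongly prognostic.

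Stratum shares, stratum effects and sparse-endpoint rates are all assumptions, as is counting separation as failure. The contradiction in the text depends on none of them.

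**What to change.** 1. In SAP 5.5.1.1, name treatment and the stratification factor as factors and weight as a covariate, and change the standardisation bracket to stratum and weight.
2. State that separation counts as non-convergence. In that case, for full-population responder endpoints, report a Mantel-Haenszel stratum-weighted risk difference with a stratified score interval before any unstratified method.
3. Keep the exact method as last resort, including for analyses within a single stratum.

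The cost is a few lines of SAP text and a standard PROC FREQ call; no new data are needed. SAP Amendment 2 is marked as preceding the Week 52 database lock, so the Week 16 analysis may already have been run. If so, the study report should state which model and which fallback step were used for each responder endpoint.

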5.5.1.2 Sensitivity analysis

5.5.1.2.1 Multiple imputation

Under MAR assumption

A linear regression model will be used to perform multiple imputation (MI) under a missing-at-random (MAR) assumption. To help preserve the relationship between outcome and covariates within each treatment a separate model will be run for each treatment. This will also help ensure that the imputation model does not make stronger assumptions on data relations than the analysis model.

The SAS code below outlines a template for the analysis where covariates and visits can be added or removed as required. To ensure that results can be replicated the data should be sorted by subject number before running the model (the data should be in horizontal format with one subject per dataset row).

```
proc mi data= seed=4572301 nimpte=100 out=mi_out;  
by treatment;  
class strata;  
fcs reg (/details);  
var strata weight value1 value2 value3;
```

run;

Where in the template code the continuous variable to be imputed is *value* (e.g. *value1* could be the baseline value and *value2* the first post-treatment measurement of the variable to be imputed.) Normally, all data collection visits during the analysis period of interest would be included in the model. Including variables using a CLASS statement instead of a BY statement should help facilitate model convergence also when the number of non-missing data points are low for some specific covariate level and visit combination. The FCS option is used to ensure that also non-monotone missing data can be handled in an appropriate way.

If convergence is not obtained the following sequential steps will be used:

1. Remove *weight*.

For a situation where several variables need to be imputed using separate models (e.g., using independent models to impute each component needed to derive a response variable *V*) a stepwise process needs to be implemented as outlined below:

1. Run the SAS code as described above for the first variable to be imputed
2. Run the SAS code as described above for the next variable to be imputed (but with the following changes: “data=*mi_out*”, “out=*mi_out2*”, “by *treatment_imputation_*”, “nimpute=1”)
3. Repeat step 2, but with input dataset equal to the output dataset from the prior step, until all *j* variables have been imputed resulting in a dataset named *mi_outj*
4. Derive the variable *V* from within *mi_outj*

The required analysis (e.g. ANCOVA) is then performed separately within each imputation dataset (as identified by variable *_imputation_*). To obtain the final result of the imputation process the analysis result from each imputation dataset needs to be combined according to Rubin’s rule as outlined below:

```
ods output parameterestimates=mi_result;  
proc mianalyze data=;  
modeleffects estimate;  
stderr estimate_se;  
run;
```

The *estimate* and *estimate_se* parameters come from the analysis model used to analyze the imputed variable within each imputation dataset (e.g., from the lsmean estimate of the treatment difference and its standard error obtained from PROC LOGISTIC or PROC MIXED)

To obtain binary response rates and confidence intervals for individual treatment groups the following process should be followed (exemplified for one visit):

```
ods output binomialprop=bin_est;  
proc freq data=;  
by treatment_imputation_;
```

```
table response / binomial (cl=wilson correct);  
run;
```

Then apply a logit transformation on the saved proportions and derive its standard error:

```
data bin_est; set bin_est;  
estimate=log(_bin_/(1-_bin_));  
estimate_se=e_bin/(_bin_*(1-_bin_));  
run;
```

[figure not shown]
The transformed binomial proportion estimates and its standard errors are then combined by applying Rubin's rules (Rubin, 1987) as described above using PROC MIANALYZE. Before presenting the combined data it needs to be transformed back as follows:

[figure not shown]
```
data mi_result; set mi_result;  
prop_est=1/(1+exp(-estimate));  
prop_lower=1/(1+exp(-lclmean));  
prop_upper=1/(1+exp(-uclmean));  
run;
```

If all responses are imputed the same as 0 (or 1) for all imputation datasets for a specific treatment or subgroup then the between-imputation-variation will be zero. The combined final response rate for the specific treatment or subgroup would be presented as seen in any of the imputed datasets together with 95% CI from Wilson's method (as obtained from PROC FREQ).

The following steps will be performed to handle special cases:

- If after imputation all responses (observed+imputed) are the same either 0 or 1 for all imputation datasets for a specific treatment or subgroup it will not be possible to perform a logit transformation and the response rate (0% or 100%) for these cases will be presented together with the 95% CI
- If after imputation the average response rate is the same across all imputed datasets (but not 0 or 1) there is no between dataset variation and Rubin's rules cannot be applied. Instead, the average response will be used with 95% CI from Wilson's method (as obtained from PROC FREQ)

Secondary analysis

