#### **12.4.4 Sensitivity analyses for primary endpoint/estimand**

Sensitivity analysis will be conducted in order to provide evidence that the results seen from the primary analysis are robust. These analyses will center on the deviations in model assumptions and the treatment of missing data.

In order to determine the robustness of the logistic regression model used for the primary analysis, ASAS40 response in active nr-axSpA participants at Week 16 will also be evaluated using a non-parametric regression ([Koch et al](#)) model with the same independent variables as the logistic regression model. In addition, further logistic regression models may be conducted which explore the impact of other baseline or disease characteristics (and respective interactions with treatment group) on response.

The impact of missing data on the analysis results of ASAS40 in active nr-axSpA participants will be assessed as well by repeating the logistic regression model using different ways to handle missing data. These may include, but are not limited to:

- Multiple imputation
- Observed data analysis

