5.1 Description of efficacy variables

Assessment of SpondyloArthritis International Society criteria (ASAS)

The ASAS response measures consist of the following assessment domains ([Sieper et al 2009](#)).

Main ASAS domains:

1. Patient's global assessment of disease activity measured on a VAS scale
2. Patient's assessment of back pain, represented by either total or nocturnal pain scores, both measured on a VAS scale
3. Function represented by BASFI average of 10 questions regarding ability to perform specific tasks as measured by VAS scale
4. Inflammation represented by mean duration and severity of morning stiffness, represented by the average of the last 2 questions on the 6-question BASDAI as measured by VAS scale

Additional assessment domains:

5. Spinal mobility represented by the BASMI lateral spinal flexion assessment
6. C-reactive protein (acute phase reactant)

ASAS Response Criteria-20% (ASAS20)

ASAS20 response is defined as an improvement of $\geq 20\%$ and ≥ 1 unit on a scale of 10 in at least three of the four main domains and no worsening of $\geq 20\%$ and ≥ 1 unit on a scale of 10 in the remaining domain with non-zero baseline assessment, or no worsening of ≥ 1 unit on a scale of 10 in the remaining domain with zero baseline assessment.

ASAS Response Criteria-40% (ASAS40)

ASAS40 response is defined as an improvement of $\geq 40\%$ and ≥ 2 units on a scale of 10 in at least three of the four main domains and no worsening at all in the remaining domain.

ASAS 5/6 improvement criteria

The ASAS 5/6 improvement is defined as an improvement of $\geq 20\%$ in at least five of all six domains.

ASAS partial remission criteria

The ASAS partial remission criteria are defined as a value not above 2 units in each of the four main domains on a scale of 10.

ASAS components

Patient's global assessment of disease activity (VAS)

The patient's global assessment of disease activity will be performed using a 100 mm visual analog scale (VAS) ranging from not severe to very severe, after the question, "*How active was your disease on average during the last week?*"

Patient's assessment of total back pain and nocturnal back pain intensity (VAS)

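### The stepwise multiple imputation carries no residual correlation between ASAS domains, so at about the planned rates it understates ASAS40 in imputed participants; imputing the domains jointly is a cheap improvement

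*SAP*

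**What the plan says.** The multiple-imputation template in SAP 5.5.1.2.1 is run separately by treatment arm with the statement "var strata weight value1 value2 value3". Here value1 to value3 are successive visits of the single variable being imputed.

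Where several variables are needed, the SAP describes a stepwise process and gives as its example "using independent models to impute each component needed to derive a response variable". The second step reads "Run the SAS code as described above for the next variable to be imputed". The listed changes are the input dataset, the output dataset, the BY statement and the number of imputations. The VAR list is not among them, so no step makes one component a predictor of another.

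The template can be adapted: "covariates and visits can be added or removed as required". On history it says "Normally, all data collection visits during the analysis period of interest would be included in the model".

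ASAS40 (SAP 5.1) is a joint event, requiring the improvement "in at least three of the four main domains and no worsening at all in the remaining domain".

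On the role of the method, Protocol 12.4.4 says "The impact of missing data on the analysis results of ASAS40 in active nr-axSpA participants will be assessed" and lists multiple imputation among the possible approaches. The SAP template stands under the sensitivity analysis in the appendix part that details the Section 2.5 models. The primary analysis itself uses non-responder imputation (SAP 2.5.3).

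**The concern.** Global assessment, pain, function and stiffness tend to improve or fail to improve together. The chance that at least three of four improve depends on that dependence as well as on each domain's own response rate. If each domain's Week 16 value is drawn from its own regression, the residual draws are independent across domains. Patterns with three or four improved domains then become too rare at response rates like those planned. If only some components are missing at a visit, the observed values of the others are not used either.

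At stake is a supportive analysis of the primary endpoint. Its task is to show what happens when missing participants are not simply counted as failures. An imputation that lowers response among them blunts that check.

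**Working it through.** **Inputs from the documents.** Planned ASAS40 rates of 29.2% (placebo) and 41.5% (secukinumab), and 120 TNF-naive participants, so 60 per arm (Protocol 12.8.1, SAP 3.1). The ASAS40 rule (SAP 5.1). The imputation template (SAP 5.5.1.2.1).

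**Assumptions, not in the documents.** Domain correlation 0.5, 0.7 or 0.85. Correlation between adjacent post-baseline visits 0.7 or 0.85. Baseline-to-post correlation 0.35. Baseline mean 7 (SD 1.5), post-baseline SD 2.4. Visits reduced to baseline and Weeks 4, 8, 12 and 16. 5-10% of participants imputed.

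**1. The plan's own figure.** With X1 ~ Bin(60, 0.415) and X2 ~ Bin(60, 0.292), P((X1 - X2)/60 > 0.0615) = 0.773 and P(X1 > X2) = 0.907. These match the stated 77.3% and 90.7%. They do not depend on the imputation, but they confirm the rates and the 60 per arm used below.

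**2. Direction.** Let p be the per-domain response, leaving aside the no-worsening condition. Under independence, P(at least 3 of 4) = 4p³(1 - p) + p⁴. The comparison is an equicorrelated probit model with correlation 0.5.

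| p | independent | correlation 0.5 |
|---|---|---|
| 0.40 | 0.179 | 0.287 |
| 0.50 | 0.312 | 0.400 |
| 0.70 | 0.652 | 0.649 |
| 0.75 | 0.738 | 0.714 |
| 0.80 | 0.819 | 0.778 |

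At correlation 0.5, p of 0.40 and 0.50 give response close to the planned 29.2% and 41.5%. There independence understates response. The sign changes near p = 0.7.

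**3. Size in imputed participants.** Four domains were simulated for 200,000 participants per arm, calibrated to the two planned rates. Week 16 was imputed from each domain's own history. The shortfall is the true rate minus the imputed rate.

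| Data available | Imputed cross-domain correlation of change (true 0.5-0.85) | Shortfall, points |
|---|---|---|
| Baseline only | 0.04-0.08 | 12.8-20.5 |
| To Week 4 | 0.07-0.32 | 8.2-18.8 |
| To Week 12 | 0.24-0.60 | 3.3-10.5 |

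Example at domain correlation 0.7 and visit correlation 0.7 with data to Week 12: placebo 29.2 - 20.0 = 9.2, secukinumab 41.6 - 33.3 = 8.3.

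Across all settings the separate models return 8.7-25.2% (placebo) and 21.2-37.8% (secukinumab). A joint model of the four domains returns 28.3-29.1% and 40.4-41.3%. A further simulation at roughly the planned rates gave 6-11 points with data to Week 8 or 12, and 13-21 with baseline only.

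**4. Whole arm.** Error = fraction imputed × shortfall. Smallest: 0.05 × 3.3 = 0.17. Largest: 0.10 × 20.5 = 2.05. So each arm is about 0.15-2 points too low, at most about 1.2 participants in 60.

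**5. Treatment difference.** Shift = (placebo fraction × placebo shortfall) - (secukinumab fraction × secukinumab shortfall).
- 10% imputed in both arms, largest case: 0.10 × (12.9 - 11.6) = 0.13 points.
- 10% placebo and 5% secukinumab: from 0.10 × 3.9 - 0.05 × 3.3 = 0.2 to 0.10 × 20.5 - 0.05 × 20.4 = 1.0 points, in favour of secukinumab.
- The reverse split gives a shift of up to 0.10 × 20.4 - 0.05 × 20.5 = 1.0 points against it.

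For scale, the planned 95% CI in scenario 2 (-0.046 to 0.293) has a half-width of (0.293 + 0.046)/2, about 17 points.

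**The case against.** **Use for ASAS40 is not stated in the visible text.** The template is generic and conditional, offers independent models as an example, and allows added covariates. SAP 2.5.4, which would say how imputation is applied to ASAS40, is not visible, and Protocol 12.4.4 says only that multiple imputation may be used. The one firm visible use is SI joint edema, a single score without this problem. This stands as a limit on certainty. The placement under the Section 2.5 models and the protocol's naming of ASAS40 still make the inference strong, and a permitted addition that nobody specifies is left to the programmer.

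**A reader might infer that the correlation is broken.** It is weakened. Each domain's own baseline and earlier visits are correlated with those of the other domains, and observed components stay as observed. Correlation is nearly lost only for early dropouts.

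**A reader might infer that the SAP contradicts its stated aim that** "the imputation model does not make stronger assumptions on data relations than the analysis model". In context that sentence explains why the model is run separately by treatment. It does not address correlation between domains.

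**A reader might infer that the result becomes indistinguishable from non-responder imputation.** The pull is in that direction, but non-responder imputation assigns 0% to these participants. With 10% imputed in an arm, a correct imputation adds 0.10 × 29.2 = 2.9 points (placebo) and 0.10 × 41.5 = 4.2 points (secukinumab). The separate models add 0.9-2.5 and 2.1-3.8 points. The check is blunted, not emptied.

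**The estimand summary is a difference in proportions, and it hardly moves.** That stands for equal missingness. Discontinuation is also non-response by definition in the primary composite variable, so this imputation is supportive only.

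**Conclusion.** The point holds as a cheap improvement to a supportive analysis. Read literally, the stepwise process omits residual dependence between domains. At roughly the planned rates it understates ASAS40 in imputed participants, by about 3-11 points when data run to Week 12 and 12-21 points with baseline only; dropouts with data only to Week 4 lie between, at about 8-19. These sizes rest on assumed correlations, and the understatement is not a general law, as the reversal above a per-domain response of about 0.7 shows.

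At arm level the error is about 0.15-2 points if 5-10% are imputed. The treatment difference changes by about 0.1 point under equal missingness and by up to about 1 point under a 10% versus 5% split. The documents do not support a claim that the primary result is biased: it uses non-responder imputation and is untouched.

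**What to change.** For multiple imputation of ASAS responses, state one of two options in SAP 5.5.1.2.1, and derive ASAS40 from the jointly imputed values:

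1. Preferred: a single FCS call by treatment with all four main domains in the VAR list, beside strata and weight.
2. Alternative: keep the stepwise process, but in the second step add the components already imputed at the same visit to the VAR list.

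The first is preferable because the second can leave a remainder. In a simulation with data missing after Week 8 and domain correlation 0.7 (not calibrated to the planned rates), true, separate and stepwise-with-added-components rates were 48.1, 38.5 and 44.8% (active) and 36.1, 26.8 and 33.3% (placebo). Over correlations of 0.5-0.8 the second option left about 2-5 points.

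Keep at least one early post-baseline visit, such as Week 4, because early dropouts are where the loss is largest. Limit the other visits. Four domains at baseline, Weeks 4, 12 and 16 give 16 variables, so each regression has 15 others plus weight and two strata indicators, 18 predictors for about 60 TNF-naive participants per arm. All eight time points to Week 16 would give 32 variables.

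The cost is a few more variables in PROC MI and a somewhat larger model. In a simulation at 60 per arm the change cut the arm-level bias from about 0.6-1.0 points to within 0.2, without loss of precision. The SAP's existing convergence step (dropping weight) can stay.
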